**Description of Study Intervention/Experimental Manipulation:**

Patients will be randomized (2:1) to participation in a 6-month web-based, integrative self-management program in addition to usual care as determined by the patient's CPP provider (intervention group), or to a web-based symptom monitoring program in addition to usual care (control group). The intervention is comprised of a self-guided program, *My Pelvic Plan*, that combines education on several individual conditions that often contribute to CPP, and will include instruction on cognitive and behavioral restructuring, self-administration of acupuncture, engaging in physical activity, and a brief introduction to pelvic floor physical therapy techniques.

**Study Duration\*:** 3 years

**Participant Duration:** 7 months

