Following enrollment, patients will complete online baseline questionnaires, which will include relevant medical and gynecologic history, pain symptoms, quality of life measures, and current treatments for pelvic pain symptoms (medications, physical therapy, etc.). After completing questionnaires, patients in the intervention group will receive access to the intervention website and those in the control group will receive access to the symptom monitoring website. Patients will be instructed to continue routine follow up and usual care with their established CPP provider throughout the study.

Patients will receive a questionnaire to evaluate pain symptoms and quality of life measures at 3-month interval (primary endpoint) and 6-month interval (secondary endpoint). After completion of 3-month questionnaire battery, we will be performing focus groups for approximately one-half of the patients in the intervention group (n=20) in order to obtain in-depth feedback regarding the program.

A participant is considered to have completed the study if they have completed the baseline questionnaire and at least the 3-month questionnaire. Patients in the intervention group may decline this invitation to participate in the focus groups and still be considered to have completed the study.

The study will conclude once all patients have completed the final 6-month questionnaires. Patients may choose to withdraw from the study at any time. If a patient withdraws before the 3-month questionnaire is sent, we will attempt to replace them with another eligible patient.

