### 6.3 MEASURES TO MINIMIZE BIAS: RANDOMIZATION AND BLINDING

Random allocation will occur in 2:1 ratio (intervention:control) utilizing permuted blocks of 4 without stratification. Allocation concealment will be ensured using computer generated central randomization and will occur after patient has signed the consent form. Enrollment will occur on a rolling basis until 69 patients have been enrolled. The study team member who generates random allocation sequence will not be involved in recruitment or enrollment.

Both patients and outcome assessors will be blinded to study group assignment. During recruitment, we will state that we are testing two different web-based approaches for self-management for chronic pelvic pain, so patients will not be aware of which study group they are enrolled in. Patients will be contacted at essentially the same intervals throughout the study period to further maintain blinding. We will attempt to blind the patient's CPP provider as to their group status but are unable to control the possibility that a patient mentions the intervention to their provider. We will ask providers not to comment about group status or discuss the intervention in detail with patients to maintain patient blinding to as great an extent as possible.

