### 9.2 SAMPLE SIZE DETERMINATION

As this is a pilot study, we have chosen to recruit a sample of 69 patients so that we can assess the feasibility of the project and to derive important effect size estimates for the definitive clinical trial that

will be conducted in a future R01 application. We are not attempting to power the analyses to detect a difference in our primary outcome (pain interference).

In addition to pain interference, we will also examine pain intensity and health-related self-efficacy to assess whether these outcomes might be more appropriate primary outcomes in an efficacy trial.

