#### 9.4.2 ANALYSIS OF THE PRIMARY ENDPOINT(S)

The primary outcome (PROMIS Pain Interference) is a continuous measure and utilizes a standardized, publicly available scoring system. We will report mean and standard deviation for each group.

Given pilot RCT design, we will use a simple posttreatment comparison of pain interference at 3-months. We will compare means with t-test. All tests will be two-sided at 5% significance level. Of note, data collected at 6-month interval will be analyzed as an exploratory outcome.

We will estimate effect size by calculating Hedges'  $g$  (rather than Cohen's  $d$  because groups are different sizes) for pain interference at 3-months, which we will use in planning for future efficacy trial.

As part of our exploratory analyses, we plan to categorize patients as "responders" vs "non-responders." "Responder" will be defined as an improvement of at least 2.5 on PROMIS Pain Interference from baseline to 3-months. We will compare differences in contributing pain conditions, pain characteristics such as Fibromyalgia Survey Score or PainDETECT, and comorbid mental health factors that may be associated responder status. We tentatively plan to use logistic regression to compare factors associated with responder status. We will use these exploratory analyses to inform structure of our future efficacy trial.

We will be using an intent to treat analysis. Patients may elect to skip questions on the questionnaire and therefore it is possible that we encounter some missing data or incomplete questionnaires. We will report the proportion of missing outcome per group and characteristics of patients with missing data. If we encounter more than 5% missing data, we plan to conduct sensitivity analyses to assess effect of missingness on results.

---

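### A 2:1 ratio cannot be built from permuted blocks of 4, so the randomisation method cannot be reproduced as written and 2:1 may not be delivered

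*Combined protocol and SAP*

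**What the plan says.** The allocation rule appears in identical words in three sections of the protocol, 4.1 (Overall Design), 6.3 (Randomization and Blinding) and 8.2 (Study Evaluation and Procedures): "Random allocation will occur in 2:1 ratio (intervention:control) utilizing permuted blocks of 4 without stratification". The synopsis repeats the ratio without a block size: "Patients will be randomized (2:1) to participation in a 6-month web-based, integrative self-management program".

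The total comes from section 6.3: "Enrollment will occur on a rolling basis until 69 patients have been enrolled". No section gives a target number per arm. The only indirect hint is in section 4.1, which plans "focus groups for approximately one-half of the patients in the intervention group (n=20".

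Section 9.2 says of the sample size: "We are not attempting to power the analyses to detect a difference in our primary outcome (pain interference". Its stated purposes are to assess feasibility and to obtain effect size estimates for a later definitive trial. Section 9.4.2 plans a t-test at 3 months and Hedges' g, the latter chosen because the arms differ in size.

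Nowhere do the documents mention varying block lengths, blocks of differing composition, or any other restricted randomisation method.

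**The concern.** A permuted block contains a fixed number of places for each arm, in random order. To hold 2:1 its length must be a multiple of 3, and 4 is not. Whoever builds the list therefore has to depart from the ratio or from the block size, and the protocol gives no basis for choosing. This is not a slip in one place, because the same sentence stands in three sections.

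Two things are at stake. The first is reporting: a sequence generation method that cannot exist cannot be reproduced, and it would be carried into the trial report as the method used. The second is arm size. If the block length was honoured and the ratio was not, the arms would differ from those that 2:1 implies. That changes the precision of Hedges' g, which the pilot is meant to supply to the next trial. It also changes the number of intervention patients available for the focus groups and utilization surveys.

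**Working it through.** **Inputs.** Ratio 2:1 (synopsis; sections 4.1, 6.3, 8.2); block length 4, unstratified (4.1, 6.3, 8.2); total 69 (6.3).

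**Step 1: can the stated rule be met?** A block of length B at 2:1 needs 2B/3 intervention and B/3 control places.
- B = 4: 2 × 4/3 = 2.67 and 4/3 = 1.33. Not possible. The available compositions are 4:0, 3:1, 2:2, 1:3 and 0:4, and none is 2:1.
- B = 3: 2 and 1. Possible; 69/3 = 23 complete blocks.
- B = 6: 4 and 2. Possible; 69/6 = 11.5, so the last block would be incomplete.

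**Step 2: what 2:1 implies for 69.** 69 × 2/3 = 46 and 69 × 1/3 = 23. This 46:23 is inferred; the protocol does not state it.

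**Step 3: what fixed blocks of 4 would give.** 69 = 17 × 4 + 1, so there are 17 full blocks and one further patient.
- 3:1 blocks: 17 × 3 = 51 and 17 × 1 = 17, plus one, giving 52:17 or 51:18.
- 2:2 blocks: 34 and 34, plus one, giving 35:34 or 34:35.
- 1:3 blocks would reverse the intended direction and are set aside, as are 4:0 and 0:4.

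**Step 4: effect on precision.** With a common SD, the standard error of the difference in means is SD × √(1/n₁ + 1/n₂). The same multiplier is, to a close approximation, the standard error of a small standardised difference.

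| Split | √(1/n₁ + 1/n₂) | SE relative to 46:23 | Variance relative to 46:23 |
|---|---|---|---|
| 46:23 | 0.2554 | reference | reference |
| 51:18 | 0.2742 | 7% larger | 15% larger |
| 52:17 | 0.2794 | 9% larger | 20% larger |
| 35:34 | 0.2408 | 6% smaller | 11% smaller |

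The direction depends on which composition was used. With 3:1 blocks there are 5 or 6 fewer controls than 23 and precision falls. With 2:2 blocks precision improves, but the intervention arm is 11 or 12 short of 46.

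**Step 5: do the documents show which figure is wrong?** They point towards the block size without proving it. The ratio is also in the synopsis, and 69 is divisible by 3 but not by 4. The reason given for Hedges' g fits unequal arms, so it speaks against 2:2, but it does not separate 2:1 from 3:1. The focus group figure does not settle it: 20 is 43% of 46, 38% of 52 and 57% of 35, all of which could pass for roughly half.

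**The case against.** The strongest reply is that this is a conflict in the text and says nothing about the list in use. A reader might infer that 2:1 will not be delivered, or that 5 or 6 controls are lost. The documents do not support that. If the list was built in blocks of 3 or 6, the ratio is delivered and only the stated block size is wrong, which is arguably the likelier explanation. Even a list in blocks of 4 need not miss 46:23: twelve 3:1 blocks, five 2:2 blocks and one control give 36 + 10 = 46 and 12 + 10 + 1 = 23. No section describes such a scheme, but it shows that the shortfall is conditional. This part of the reply stands.

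It is also fair to say that the statistical damage is limited. Random allocation at a fixed 3:1 or 1:1 ratio would still be unbiased, the t-test and Hedges' g would remain valid, and the trial makes no power claim that could fail. Sections 4.1, 7.2 and 8.2 also plan to replace patients who withdraw before the 3-month questionnaire is sent. The number randomised may therefore exceed 69, and the final split may differ somewhat from 46:23 under any scheme. This stands too.

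What the reply does not remove is the contradiction. No other section resolves it, and the unpowered design does not excuse it, because the effect size and its precision are what the pilot is meant to deliver.

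**Conclusion.** The point holds as an internal contradiction that needs correcting. The allocation method in sections 4.1, 6.3 and 8.2 is arithmetically impossible, so it cannot be generated or reproduced as written, and the 2:1 ratio may not be delivered. The impossibility needs no assumption beyond the ordinary meaning of a permuted block.

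The size of the consequence is conditional. It assumes fixed-composition blocks of 4 and exactly 69 patients, and it is measured against an inferred 46:23. On those terms the standard error lies between about 6% smaller and 9% larger than under 2:1. It would be wrong to conclude that precision must fall, that the allocation has in fact failed, or that the treatment comparison is biased. The documents show neither the list nor the achieved arm sizes.

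**What to change.** **If no list is in use yet:** keep 2:1 and, in sections 4.1, 6.3 and 8.2, replace the block size with lengths that are multiples of 3, allocated 2:1 within each block. Any multiple of 3 removes the contradiction. Mixing lengths 3 and 6 is one option and makes the next assignment harder to predict than fixed blocks of 3. With free mixing, however, patient 69 can fall halfway through a block of 6. The first 66 patients are then 44:22 and the last three can add 1:2, 2:1 or 3:0, ending at 45:24, 46:23 or 47:22. If exactly 46:23 is wanted, constrain the sequence so that a block ends at 69. State the target per arm in section 9.2.

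**If randomisation has begun:** do not regenerate the list. Have someone independent of recruitment and outcome assessment check it, correct the three sections to the ratio and block size actually used (and the synopsis if the ratio differs), and report the actual arm sizes.

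**Cost:** one sentence in three places, plus either generating the list correctly or checking the existing one. No additional patients or data are needed.

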### 6.4 STUDY INTERVENTION/EXPERIMENTAL MANIPULATION ADHERENCE

Each month, we will ask intervention group participants to indicate which skills they have utilized in the past month. However, we are unable to track website utilization for individual patients based on the current website design.

Relative to questionnaires, we will require completion of baseline questionnaires in order to participate in the study. We will not dismiss patients from participating if they do not complete questionnaires but will send multiple reminders and monetary incentives for participating.

### 6.5 CONCOMITANT THERAPY

All patients will receive usual care as recommended by their CPP provider throughout the study. Our group of CPP providers utilize a fairly similar, multimodal approach for managing chronic pelvic pain. This commonly includes hormonal suppression, physical therapy, muscle relaxants, and centrally acting neuropathic medications. The specific strategies are highly dependent on the conditions contributing to pain symptoms in an individual patient. Of note, we utilize shared decision-making with patients, which means that some patients choose not to utilize a treatment that we may typically recommend as first-line therapy for a particular condition. Therefore, we anticipate that there will be variability in treatments

utilized across patients. We will assess treatments utilized at each questionnaire time point and will perform exploratory analyses to assess impact on primary and secondary outcomes.

While we will exclude patients who have undergone gynecologic surgery within 3 months of screening visit, plan to undergo gynecologic surgery within 6 months following screening visit, are currently pregnant, at time of screening visit, patients will be able to proceed with any intervention determined to be necessary by their medical providers, including surgery and medication changes, without being excluded from our analysis. We also will not exclude patients who become pregnant during the study. We will collect data on interim surgery or medication changes at the 6-month follow up period.

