## 1.2 SCHEMA

### Flow Diagram

### 1.3 SCHEDULE OF ACTIVITIES

	Pre-consent	0 month Day 0 $\pm$ 14	1 month Day 30 $\pm$ 14	2 month Day 60 $\pm$ 14	3 month Day 90 $\pm$ 14	4 month Day 120 $\pm$ 14	5 month Day 150 $\pm$ 14	6 month Day 180 $\pm$ 14
Review eligibility	x	x						
Consent		x						
Randomization		x			x			
Adverse Event Reporting		x	x	x	x	x	x	x
Intervention								
Access My Pelvic Plan (Intervention group)		x	x	x	x	x	x	x
Access Monitoring Progress (Control group)		x	x	x	x	x	x	x
Outcome evaluation								
Questionnaire		x			x			x
Current treatment survey		x						x
Utilization survey (Intervention group)			x	x	x	x	x	x
Focus group (n=20, Intervention group)					x			

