## 2.3 RISK/BENEFIT ASSESSMENT

### 2.3.1 KNOWN POTENTIAL RISKS

*Breach of confidentiality:* Participation in this study poses a risk for breach of confidentiality. Several measures have been taken to reduce the risk of breach of confidentiality. These include training of study team members, electronic and physical security measures for data capture and storage and collecting a minimum of identifiable information for each individual project. Breach of confidentiality will be considered a “definitely related” Serious Adverse Event. As such, it will be reported to the University of Michigan IRB within 7 days of occurrence, and a remediation plan will be put in place immediately.

*Discomfort associated with being asked personal questions about health history and the completion of questionnaires:* Any participant becoming distressed while completing questionnaires will be encouraged to seek clarification of any questions that they find to be unclear or troubling. All participants are told that they have the option to terminate participation without penalty and/or will be assisted in arranging medical/ psychiatric help including, if necessary, emergency treatment if needed.

*Symptom exacerbation:* We do not anticipate that the *My Pelvic Plan* program is likely to place patients at an increased risk of symptom exacerbations. Cognitive and behavioral programs have been shown to be low risk for adverse events. However, we will discuss that new activities, such as physical therapy and exercise, sometimes precipitate a temporary increase in myofascial pain, and will offer basic anticipatory guidance. This is a well-described phenomenon and is not unique to this program. Our CPP provider have extensive expertise in determining whether exacerbations are typical given possible triggers and can offer individual guidance on whether additional evaluation is warranted.

During the study period, all patients will receive usual care as determined by their CPP provider and PCP. While we will not enroll patients who are planning to undergo surgery during the study period, patients will be able to proceed with any intervention determined to be necessary by their medical providers, including surgery and medication changes, without being excluded from our analysis. We will collect data on interim surgery or medication changes at the 3 and 6-month follow up periods.

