Patients will receive a questionnaire battery at 3-month interval (primary endpoint) and 6-month interval (secondary endpoint). Patients will receive an email with a link to questionnaires at 3 months and again at 6 months. The 6-month questionnaire will also include questions regarding current treatments for pelvic pain symptoms, including interval surgery.

After completion of 3-month questionnaire battery, we will be performing focus groups for approximately one-half of the patients in the intervention group (n=20) in order to obtain in-depth feedback regarding the program. We will attempt to include an intentionally diverse group of

participants for these focus groups, with intentional recruitment to reflect diversity in age, race, geographic location and pelvic pain conditions. These sessions will focus on skills and modules that were most impactful and whether participants believe that combining the intervention with an individual coach or an online community might be beneficial.

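### The documents disagree on whether concurrent-treatment data are collected at month 3, the primary time point

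*Combined protocol and SAP*

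**What the plan says.** Two statements put treatment data at month 3. Section 2.3.1: "We will collect data on interim surgery or medication changes at the 3 and 6-month follow up periods". Section 6.5, first paragraph: "We will assess treatments utilized at each questionnaire time point and will perform exploratory analyses to assess impact on primary and secondary outcomes". Section 5.5 fixes the questionnaires as baseline, 3 months and 6 months.

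Three places do not put it there. Section 6.5, last sentence: "We will collect data on interim surgery or medication changes at the 6-month follow up period". Section 8.2, under the intervention group: "The 6-month questionnaire will also include questions regarding current treatments for pelvic pain symptoms, including interval surgery". In the Schedule of Activities (1.3), the row "Current treatment survey" is marked at month 0 and month 6, while the general questionnaire row is marked at months 0, 3 and 6.

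The primary analysis is set at month 3. In section 9.4.2, "we will use a simple posttreatment comparison of pain interference at 3-months", by t-test. The same section places Hedges' g and the responder definition (an improvement of at least 2.5 from baseline) at month 3.

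**The concern.** Sections 2.3.1 and 6.5 let patients have surgery or change medication during the trial and stay in the analysis. The investigators evidently see co-treatment as a threat to interpretation: section 8.1 leaves out new patients because their many new treatments would be hard to separate from the effect of the program. Returning patients still visit about every 3 to 4 months (8.2), so some treatment decisions may fall before month 3.

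Two things depend on knowing about those decisions. One is the exploratory analysis promised in 6.5, which names the primary outcome. The other is the responder work in 9.4.2 and 9.4.9. A patient who starts another therapy in the first three months and improves by 2.5 points is counted as a responder, and without treatment data at month 3 that patient cannot be told apart from one who responded to the program. Staff would build the questionnaires from the Schedule and section 8.2, and those are the parts that leave month 3 out.

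**Working it through.** The plan has no figure to reproduce, and no arithmetic settles the point. The check is a comparison of every place that deals with treatment data.

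| Place | Content | Baseline | Month 3 | Month 6 |
|---|---|---|---|---|
| 2.3.1 | interim surgery or medication changes | not addressed | yes | yes |
| 6.5, first paragraph | treatments used | yes | yes | yes |
| 6.5, last sentence | interim surgery or medication changes | not addressed | not named | yes |
| 8.2 (baseline text; intervention group) | current treatments; interval surgery at month 6 | yes | not named | yes |
| 1.3 Schedule, treatment survey row | current treatments | yes | no | yes |

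**Is it a true conflict?** Yes, on two separate items. Section 2.3.1 and the last sentence of 6.5 describe the same item, interim changes, with different timing. The first paragraph of 6.5 and the Schedule row describe the same item, treatments in use, also with different timing.

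**What each reading gives.** There are two post-baseline questionnaires. Under 2.3.1 and the first paragraph of 6.5, both carry treatment data. Under the Schedule, one of the two does, and the one without is the primary time point.

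**What else exists by month 3 if the Schedule governs.**
- Section 3 lists an opioid/benzodiazepine self-report and a cannabis survey at 3 and 6 months.
- Sections 8.4.1 and 8.4.2 make an emergency visit, scheduled gynecologic surgery, urgent or emergent surgical evaluation and hospitalization reportable events when a pain exacerbation prompts them. The Schedule has adverse-event reporting from month 0 through month 6, and 8.4.4 records time of onset. Capture rests mainly on self-report, with no active search of medical records.
- Section 6.5 describes usual care as commonly hormonal suppression, physical therapy, muscle relaxants and centrally acting neuropathic drugs. None of these is covered by the two routes above, and neither is surgery not prompted by an exacerbation.

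**Can the month-6 survey stand in?** Only in part.
- Nominal visits are day 90 and day 180. A change made between day 0 and day 90 would be reported 180 − 90 = 90 to 180 − 0 = 180 days later.
- The plan does not say that month-6 reports carry dates, so a change could not be assigned reliably to before or after month 3.
- Sections 4.1 and 8.2 count a participant as complete after the 3-month questionnaire, and 7.3 calls the 6-month one inessential for the primary outcome. A patient with full primary-outcome data could therefore have no post-baseline treatment survey. Carrying the last observation forward (9.3) does not help, because the last treatment survey would be the baseline one.

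**What is and is not touched.** The t-test and Hedges' g use only the month-3 scores, so their computation does not change. The exploratory treatment analysis, and what can be said about responders, do depend on these data.

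**The case against.** The strongest reply is that month-3 collection is stated twice and that section 8.2 says the 6-month questionnaire will include treatment items without saying that only that questionnaire will. On this view the Schedule merely lacks a mark. That reply stands as far as it goes: month-3 collection is contradicted, not settled as absent. It is also a reason to correct the text, since the documents alone do not show which version will be built.

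A reader might infer that the promised analysis is impossible. The documents do not support that. Section 6.5 promises an analysis of treatments used, not specifically of changes. Baseline treatments are collected (4.1, 8.2) and can be related to the 3-month outcome, and dated questions at month 6 could recover some early changes.

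A reader might also infer that nothing about co-treatment is known at month 3. The opioid/benzodiazepine and cannabis measures and the adverse-event route for exacerbation-driven surgery show otherwise.

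Design features reduce the problem as well. Only returning patients are recruited (8.1), and gynecologic surgery planned within 6 months is an exclusion (5.2). A visit every 3 to 4 months need not fall before month 3 or bring a change in treatment.

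Finally, the trial is a pilot that section 9.2 says is not powered for the primary outcome, and the affected analysis is exploratory. That limits the weight of the point but does not remove it. The pilot's stated purpose is to generate hypotheses about who responds, and that is where the missing data would be felt.

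**Conclusion.** The point holds as an internal contradiction with a practical consequence. Sections 2.3.1 and 6.5 (first paragraph) promise month-3 treatment data; the Schedule, section 8.2 and the last sentence of 6.5 do not provide for it. If the Schedule is followed, the exploratory analysis of treatments against the 3-month outcome, and the interpretation of 3-month responder status, would lack general co-treatment data. Some month-3 completers could have no treatment survey after baseline. The primary comparison is not affected.

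The size cannot be expressed as a shift in the treatment difference. A reader might try to do so by assuming an imbalance in new treatments and an effect per treatment, then comparing the product with 2.5 points. The documents give neither input, and they use 2.5 as a within-patient responder threshold, not as a margin between arms. If the program itself changes care-seeking, the resulting difference in co-treatment is also part of the intent-to-treat effect, not a bias to be removed.

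The conclusion assumes that the questionnaires follow the Schedule and section 8.2, and that the month-6 items are not dated, on which the plan is silent. It merits correction because the remedy is cheap and data not asked for at month 3 cannot be fully recovered later.

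**What to change.** - Add the existing current treatment survey to the 3-month online questionnaire in both arms, with interval surgery and medication changes and the date of each. Ask for dates at month 6 too.
- Mark month 3 in the treatment survey row of the Schedule of Activities.
- Align sections 2.3.1, 6.5 and 8.2 with that row. Section 8.2 names the 6-month treatment items only under the intervention group, so state there that the control group receives the same items at the same times.
- Report co-treatment by arm at 3 and 6 months as description. It arises after randomisation, so it should not be used to adjust the primary comparison.

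The cost is a few extra items in a questionnaire that patients already complete, with slightly more burden and some editing of the protocol. If the investigators prefer not to collect these data at month 3, sections 2.3.1 and 6.5 should say so, and the promised exploratory analysis should be limited to what baseline and month-6 data can support.
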